	
survival events have been observed. At the second interim analysis, if the OS efficacy boundary is crossed, the trial will be stopped for efficacy. Otherwise, conditional power will be calculated to determine the overall survival event size for final analysis.
 
Patients will be randomized at a 1:1 ratio to receive one of two treatments:
 
 
• Arm A: Bempegaldesleukin plus pembrolizumab every 3 weeks (q3w) for up to 35 cycles (approximately 2 years).
 
• Arm B: Pembrolizumab monotherapy q3w for up to 35 cycles (approximately 2 years).
 
 
Randomization will be stratified according to the following factors:
 
 
1. Disease status (metastatic vs recurrent only).
 
2. PD-L1 tumor expression determined by PD-L1 immunohistochemistry (IHC) 22C3 PharmDx (CPS <math>\geq 20</math> vs CPS 1-19) at either a local or the central laboratory.              Note: CPS is the number of PD-L1 staining cells (tumor cells, lymphocytes, macrophages) divided by the total number of viable tumor cells, multiplied by 100. The specimen should be considered to have PD-L1 expression if CPS <math>\geq 1</math>.
 
3. Human papillomavirus (HPV) status for oropharyngeal cancer determined by p16 IHC (positive vs negative). For patients with cancers of the oral cavity, hypopharynx, and larynx, HPV status is considered HPV negative.
 
 
Patients who attain a complete response may consider stopping study drug if they meet criteria for holding therapy. Patients who stop study drug after receiving 35 cycles (approximately 2 years) of study drug for reasons other than disease progression or intolerability, or patients who attain a complete response and stop study drug may be eligible for up to 17 cycles (approximately 1 year) of retreatment upon experiencing Investigator-determined radiographic disease progression. The decision to retreat will be at the discretion of the Investigator only if the patient meets the criteria for retreatment and the trial is ongoing.
 
After the end of treatment, each patient will be followed for 90 days after the last dose of all study drug(s) for AE monitoring, including serious AEs [SAEs] and AEs of special interest [AESI]. Patients who discontinue for reasons other than centrally verified disease progression will have post-treatment follow-up for disease status until disease progression is verified by the central imaging vendor, initiating a non-study cancer treatment, withdrawing consent, or becoming lost to follow-up. All patients will be followed for overall survival until death, the patient withdraws consent, the patient is lost to follow-up, or the study is terminated by the Sponsor.
 
The Sponsor estimates that the study will be fully enrolled within approximately 25 months. Analyses are anticipated at the following times (relative to the first patient’s randomization date): approximately 14 months for the first interim analysis, approximately 32 months for the second interim analysis, and approximately 38 to 52 months for the final analysis for overall survival.

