	
 
• Have histologically or cytologically-confirmed recurrent or metastatic HNSCC that is considered incurable by local therapies. 
 
○ No prior systemic therapy for recurrent or metastatic disease. Systemic therapy given as part of multimodal treatment for locally advanced disease is allowed if completed more than 6 months prior to signing consent.
 
○ The eligible primary tumor locations are oropharynx, oral cavity, hypopharynx, and larynx.
 
○ Patients may not have a primary tumor site of nasopharynx (any histology) and/or unknown primary.
 
 
 
• Have measurable disease based on RECIST 1.1 as determined by the local site Investigator. Tumor lesions situated in a previously irradiated area are considered measurable if progression has been shown in such lesions since irradiation.
 
• Eastern Cooperative Oncology Group (ECOG) Performance Status of 0 or 1.
 
• Tumor tissue from a core, incisional, or excisional biopsy (fine needle aspirates are not acceptable) to the central laboratory for determination of PD-L1 status (if not determined at local laboratory) [REDACTED]. A newly obtained biopsy is strongly preferred, but archival tumor biopsy may be used and provided (see Section 8.3.1).
 
• The tumor must have positive PD-L1 expression (ie, CPS <math>\geq</math> 1) as determined with the PD-L1 IHC 22C3 PharmDx diagnostic kit at either a local or central laboratory.
 
• Patients with oropharyngeal cancer: must have results from testing of HPV status defined as p16 IHC testing using CINtec® p16 Histology assay (Ventana Medical Systems Inc., Tucson AZ). If HPV status was previously tested using this method, no additional testing is required. Note: 
 
○ If local p16 testing results are not available, or cannot be assessed by the specified method, a tumor tissue sample may be submitted to the central laboratory for p16 testing.
 
 
 
 
Patients with oral cavity, hypopharynx, or larynx cancers: HPV testing by p16 IHC is not required as by convention these tumor locations are assumed to be HPV negative.
 
Key Exclusion Criteria:
 
 
• Has disease that is suitable for local therapy administered with curative intent.
 
• Has progressive disease within 6 months of completion of curatively intended systemic treatment for locoregionally advanced HNSCC.
 
• Has had radiation therapy (or other non-systemic therapy) within 2 weeks prior to initiation of study drug, or patient has not fully recovered (ie, <math>\leq</math> Grade 1 or at baseline) from AEs due to a previously administered treatment. A 1-week washout is permitted for palliative radiation (<math>\leq</math> 2 weeks of radiotherapy) to non-central nervous system (CNS) disease. Note: 
 
○ Patients with <math>\leq</math> Grade 2 neuropathy or <math>\leq</math> Grade 2 alopecia are an exception to this criterion and qualify for the study.
 
○ If patient received major surgery, they must have recovered adequately from the toxicity and/or complications from the intervention prior to starting therapy.
 
 
 
• Has a life expectancy of less than 3 months and/or has rapidly progressing disease (eg, tumor bleeding, uncontrolled tumor pain) as determined by Investigator.
 
• Has a known additional malignancy that is progressing or has required active treatment within 5 years prior to the first dose of study drug with the exception of: curatively treated basal cell carcinoma of the skin, squamous cell carcinoma of the skin, curatively resected in situ cervical cancer, and curatively resected in situ breast cancer.
 

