Statistical Methods:	
General Considerations: In general, continuous data will be summarized by descriptive statistics, including number of patients, mean, standard deviation, median, minimum, and maximum. Categorical data will be summarized by the number and percentage of patients.
 
Efficacy:
 
As a primary efficacy endpoint, ORR will be tested at an alpha level of 0.001. The Cochran Mantel Haenszel (CMH) test statistic will be used to compare the proportion of patients with an objective response between the 2 treatment arms.
 
As a primary efficacy endpoint, OS will be evaluated at an alpha level of 0.049 if ORR is not significant and 0.05 if ORR is significant. The stratified log-rank test statistic with prespecified weights will be used to compare OS between the 2 treatment arms. A stratified Cox proportional hazards model with treatment as the single covariate will be used to estimate the hazard ratio and corresponding 95% confidence interval (CI). The Kaplan-Meier method will be used to further summarize OS, including Kaplan-Meier curves, medians with corresponding 95% CIs, etc.
 
The first interim analysis will occur at least one month after the last patient of the Phase 2 portion has been randomized into the study. At the first interim analysis, ORR will be assessed for futility:
 
 
• ORR futility assessment (ie, difference in ORR proportions is <math>\geq 0\%</math> [bempegaldesleukin plus pembrolizumab minus pembrolizumab monotherapy]) will serve as a gate to proceed to the Phase 3 portion of the study.
 
 
If the DMC determines that the study should continue based on the prespecified futility boundary, Phase 3 of the study will begin following an expected 4-month enrollment pause for the first interim analysis readout. At the second interim analysis when approximately 500 patients have been randomized and about 231 OS events have been observed, the following tests will be conducted (if the actual number of events at the time of the analysis is different from the planned one, the actual alpha and statistical significance level will be adjusted using O'Brien and Fleming alpha spending function):
 
 
• If ORR is not significant at the second interim analysis, OS will be tested at an overall alpha level of 0.049 and at <math>\alpha = 0.021</math> at the second interim analysis.
 
• If ORR is significant at the second interim analysis, the fallback method will be used and OS will be tested at an overall alpha level of 0.05 at <math>\alpha = 0.022</math> at the second interim analysis.
 
 
For the final analysis, the adaptive method in Liu and Hu (Liu 2016) and Mehta and Pocock (Mehta 2011) will be used to determine the number of OS events needed to target approximately 85% to 90% conditional power for the final analysis. The minimum and maximum number of OS events for the final analysis are 298 and 393, respectively.
 
At the final analysis, the primary analysis of OS to claim statistical significance will be based on the weighted combination version of the stratified log-rank test with prespecified weights (Lehmacher 1999). Statistical significance level for the final analysis is 0.043 or 0.044 depending on whether ORR is significant at the second interim analysis. Prespecified

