### 3.2.3 Prospective Stratification

Randomization will be stratified by 3 factors:

- Disease status (metastatic vs recurrent only). In the KEYNOTE-048 trial, metastatic versus recurrent only disease status demonstrated a prognostic value for patient survival ([Burtness 2019](#)).
- PD-L1 tumor expression determined by PD-L1 IHC (CPS  $\geq$  20 vs CPS 1-19). The KEYNOTE-048 trial demonstrated a statistically significant improvement in OS in the subgroup of patients with CPS  $\geq$  1 randomized to single-agent pembrolizumab. The median OS for CPS  $\geq$  1 in months was 12.3 (95% CI: 10.8, 14.9). The median OS for the CPS  $\geq$  20 subgroup in months was 14.9 (95% CI: 11.6, 21.5) for single agent pembrolizumab ([Burtness 2019](#)). In an exploratory subgroup analysis, CPS 1 – 19 median OS was 10.8 months (95% 9.0, 12.6) for single agent pembrolizumab ([Merck 2020](#)).
- HPV status (positive or negative) for patients with head and neck cancer of the oropharynx. The favorable prognostic significance of HPV-positive head and neck cancers in the oropharynx has been increasingly established ([Fakhry 2008](#)). Preliminary data of single agent pembrolizumab in head and neck cancer patients in KEYNOTE-012 demonstrate efficacy in both HPV-positive and HPV-negative patients. Investigator site assessment of HPV using IHC staining for the p16 protein will be used for the patients with oropharyngeal cancer prior to randomization.

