## 5.0 SELECTION OF STUDY POPULATION

### 5.1 Inclusion Criteria

An eligible patient must meet all of the following criteria:

1. Provide written, informed consent to participate in the study and follow the study procedures. The Investigator takes responsibility for ensuring that all vulnerable patients are protected and participate voluntarily in an environment free from coercion or undue influence. The patient may also provide consent for additional research (described in Section 8.3.3). However, the patient may participate in the study without participating in additional research.
2. Male or female patients, age 18 years or older at the time of signing the informed consent form (ICF).
3. Have histologically or cytologically-confirmed recurrent or metastatic HNSCC that is considered incurable by local therapies.
  - a. No prior systemic therapy for recurrent or metastatic disease. Systemic therapy given as part of multimodal treatment for locally advanced disease is allowed if completed more than 6 months prior to signing consent.
  - b. The eligible primary tumor locations are oropharynx, oral cavity, hypopharynx, and larynx.
  - c. Patients may not have a primary tumor site of nasopharynx (any histology) and/or unknown primary.
4. Have measurable disease based on RECIST 1.1 as determined by the local site Investigator. Tumor lesions situated in a previously irradiated area are considered measurable if progression has been shown in such lesions since irradiation.
5. Eastern Cooperative Oncology Group (ECOG) performance status of 0 or 1 (see Appendix 3).
6. Provide tumor tissue from a core, incisional, or excisional biopsy (fine needle aspirates are not acceptable) to the central laboratory for determination of PD-L1 status (if not determined at local laboratory) [REDACTED]. Repeat samples may be required if adequate tissue is not provided for assessment of PD-L1 status. A newly obtained biopsy is strongly preferred, but archival tumor biopsy may be used and provided (see Section 8.3.1).
7. The tumor must have positive PD-L1 expression (ie, CPS  $\geq$  1) as determined by a local or the central laboratory with the IHC 22C3 PharmDx diagnostic kit.

8. Patients with oropharyngeal cancer: must have results from testing of HPV status defined as p16 IHC testing using CINtec® p16 Histology assay. If HPV status was previously tested using this method, no additional testing is required. Note:

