## 11.0 STATISTICAL PLAN

### 11.1 General Considerations

In general, continuous data will be summarized by descriptive statistics, including number of patients, mean, standard deviation, median, minimum, and maximum. Categorical data will be summarized by the number and percentage of patients. Unless otherwise specified, data will be summarized by treatment arm.

All efficacy evaluations will be analyzed using the intent-to-treat (ITT) population unless otherwise specified, and all safety endpoints will be summarized using the Safety population. In general, the following three stratification factors will be used in stratified analysis in comparing response rates and survival curves of the two arms (bempegaldesleukin plus pembrolizumab versus pembrolizumab), and in Cox proportional hazard analysis unless otherwise specified: disease status (metastatic vs recurrent only), PD-L1 tumor expression (CPS  $\geq$  20 vs CPS 1-19) and HPV status (positive vs negative).

The detailed description of analysis methods will be provided in the statistical analysis plan (SAP).

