### 11.5 Efficacy Analyses

#### 11.5.1 Primary Efficacy Analyses

ORR is defined as the percentage of patients with a confirmed best overall response of CR or PR by RECIST 1.1 per BICR in the ITT population. As a primary efficacy endpoint, ORR will be tested at an overall alpha level of 0.001. The Cochran Mantel Haenszel (CMH) test statistic will

be used to compare the proportion of patients with an objective response between the 2 treatment arms.

The ORR difference between the two treatment arms with its 95% and 99.5% confidence intervals (CIs) will be calculated by the CMH test statistic using the normal approximation. The ORR and its corresponding 95% exact CI will also be calculated by Clopper-Pearson method for each arm. Patients who do not have on-study tumor assessments to evaluate response status will be counted as non-responders.

Overall survival (OS) is defined as the time between the date of randomization and the date of death due to any cause. A patient who does not have a date of death will be censored on the last date for which the patient was known to be alive.

As another primary efficacy endpoint, OS will be evaluated at an overall alpha level of 0.049 if ORR is not significant and at 0.05 if ORR is significant. The regular stratified log-rank test will be used at IA2 to compare overall survival between the two treatment arms. At the final analysis, the weighted combination version of the stratified log-rank test with prespecified weights (Lehmacher 1999) will be used to compare overall survival between the two treatment arms. A stratified Cox proportional hazards model with treatment as the single covariate will be used to estimate the hazard ratio and corresponding 95% CI. The weighted combination approaches as specified in Brannath et. al. (Brannath 2006) will be performed as an exploratory analysis. The Kaplan-Meier method will be used to summarize overall survival per arm, including Kaplan-Meier curves, medians with corresponding 95% CIs, etc.

At the first interim analysis, ORR will be assessed for futility: ORR futility assessment (ie, the difference in ORR proportions is  $\geq 0\%$  [bempegaldesleukin plus pembrolizumab minus pembrolizumab monotherapy]) will serve as a gate to proceed to the Phase 3 portion of the study.

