### 11.5.2 Secondary Analyses

**Progression-free survival (PFS):** defined as the time between the date of randomization and the first date of documented disease progression using RECIST 1.1 per BICR or death due to any cause, whichever comes first. Stratified log-rank test will be used to compare PFS between the two treatment arms. PFS will be tested following OS significance and at the same significant level as OS. A stratified Cox proportional hazards model with treatment as the single covariate will be used to estimate the hazard ratio and corresponding 95% CI for PFS. The Kaplan-Meier method will be used to summarize PFS, including Kaplan-Meier curves, medians with corresponding 95% CIs, etc.

The censoring rules for PFS will be detailed in the SAP.

[REDACTED]

[REDACTED]

[REDACTED]

[REDACTED]

[REDACTED]

[REDACTED]

[REDACTED]

[REDACTED]

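### The OS and PFS hazard ratios come from a stratified Cox model that leaves out Screening ECOG (0 vs 1); if ECOG is prognostic, the reported hazard ratio is pulled toward 1 and exposed to chance imbalance

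*Protocol*

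**What the plan says.** The OS hazard ratio is specified in the synopsis (Statistical Methods): "A stratified Cox proportional hazards model with treatment as the single covariate will be used to estimate the hazard ratio". Section 11.5.1 specifies it again: "A stratified Cox proportional hazards model with treatment as the single covariate". Section 11.5.2 uses the same kind of model to "estimate the hazard ratio and corresponding 95% CI for PFS".

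Section 11.1 fixes the strata: "the following three stratification factors will be used in stratified analysis in comparing response rates and survival curves of the two arms". They are disease status, PD-L1 CPS (20 or more vs 1-19) and HPV status. These are also the randomization factors. Section 3.2.3 ("Randomization will be stratified by 3 factors") supports disease status and HPV by their prognostic value, and CPS by survival differences.

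ECOG appears as an entry criterion in Section 5.1: "Eastern Cooperative Oncology Group (ECOG) performance status of 0 or 1". Table 1 schedules it at Screening (Day -28 to -1) and before each dose. It has no role in the readable description of the OS and PFS models.

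The OS significance decision does not come from the Cox model. Under Section 11.5.1 it rests on the stratified log-rank test at the second interim analysis (IA2) and on its weighted combination version at the final analysis.

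**The concern.** A baseline value with two levels, recorded before treatment is assigned, is available for every patient and is not used. If ECOG 1 patients die sooner than ECOG 0 patients, two things follow for a Cox model that omits ECOG.

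- **Attenuation.** Even with perfect balance, the treatment hazard ratio is pulled toward 1 compared with the hazard ratio within ECOG levels.
- **Chance imbalance.** ECOG is not a randomization factor, so the arms can differ by chance, and that difference carries into the reported hazard ratio.

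At stake is the headline OS and PFS effect estimate. The trial is open-label, so an ECOG adjustment added after an imbalance had been seen would look data-driven. That is the reason to prespecify it.

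**Working it through.** **1. The plan's own figure.** Inputs from Section 11.2.2: hazard ratio 0.7, two-sided alpha 0.049, 85% power, 298 events; the same section also gives 86% for 298 events.

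- Schoenfeld: events = 4(z₁ + z₂)²/(ln HR)² = 4(1.9685 + 1.0364)²/(0.3567)² = 284. Freedman's formula gives 290.
- Power at 298 events, fixed design: Φ(√298/2 × 0.3567 − 1.9685) = Φ(1.110) = 86.6%.
- Two looks at 231 and 298 events with O'Brien-Fleming-type spending: interim alpha 0.0213, final level 0.0427, power 86.0%. The plan states 0.021, 0.043 and 86%.

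The design figures reproduce.

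**2. Attenuation, by simulation.** From the documents: 500 patients 1:1, control median 12.3 months, hazard ratio 0.70, analysis at 298 events, two-sided 0.049. Assumed: 40% or 60% ECOG 1; ECOG hazard ratio 1.0 to 2.0; three binary strata with modest effects; exponential survival; uniform entry over 25 months. There were 1,500 trials per row, with a single Wald test and no interim. The Monte Carlo SE of each power figure is about √(0.85 × 0.15/1500) = 0.9 points; adjusted and unadjusted results come from the same simulated trials.

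| ECOG HR | ECOG 1 share | HR without / with ECOG | SE(log HR) without / with | Power without / with |
|---|---|---|---|---|
| 1.0 | 40% | 0.701 / 0.701 | 0.1187 / 0.1189 | 85.3% / 84.7% |
| 1.0 | 60% | 0.700 / 0.699 | 0.1187 / 0.1189 | 84.7% / 84.5% |
| 1.3 | 40% | 0.704 / 0.702 | 0.1186 / 0.1189 | 83.2% / 83.4% |
| 1.3 | 60% | 0.702 / 0.700 | 0.1186 / 0.1189 | 84.3% / 84.7% |
| 1.6 | 40% | 0.705 / 0.699 | 0.1186 / 0.1190 | 83.4% / 84.9% |
| 1.6 | 60% | 0.703 / 0.697 | 0.1186 / 0.1189 | 83.9% / 86.2% |
| 2.0 | 40% | 0.715 / 0.703 | 0.1185 / 0.1190 | 80.0% / 83.5% |
| 2.0 | 60% | 0.713 / 0.700 | 0.1185 / 0.1190 | 81.4% / 86.1% |

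The SE does not fall; it rises very slightly. The power change comes from the estimate. In the last row, |ln 0.7134|/0.1185 = 2.850 without ECOG and |ln 0.6995|/0.1190 = 3.003 with it. Subtracting 1.9685 gives Φ(0.88) = 81.1% and Φ(1.03) = 85.0%, close to the simulated values.

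A second simulation (staged accrual with the enrollment pause, 60% ECOG 1, 2,500 trials per scenario) gave 85.7% vs 86.6% at an ECOG hazard ratio of 1.5, and 82.8% vs 85.8% at 2.0. Together the two put the gain at 2.0 at 3.0 to 4.7 points.

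**3. Chance imbalance.** With 250 per arm and 40% or 60% ECOG 1, the SD of the difference in ECOG 1 share is √(0.6 × 0.4 × 2/250) = 0.044. A 2-SD imbalance is 0.088. To first order the shift in log HR is the imbalance times ln(ECOG HR):

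- ECOG HR 1.5: 0.088 × 0.405 = 0.036, or 0.036/0.119 = 0.3 SE.
- ECOG HR 2.0: 0.088 × 0.693 = 0.061, or 0.061/0.119 = 0.5 SE. Around an unadjusted centre of 0.714 this gives 0.714 × e^(±0.061), about 0.76 or 0.67.

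An imbalance of 2 SD or more, in either direction, arises in about 1 trial in 20.

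PFS was not simulated. The mechanism is the same, but no size is claimed for it.

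**The case against.** The case against is substantial.

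- **Precision.** A reader might infer that omitting ECOG costs precision. It does not: SE(log HR) is about 0.1186 without ECOG and 0.1189 with it, so the interval on the log scale is no narrower after adjustment.
- **Confirmatory power.** A reader might infer that the OS test loses power through this sentence. It does not, because the log-rank test decides OS and changing the Cox model alone changes that decision by nothing. The power figures above apply only to a test that itself adjusts for ECOG.
- **A power shortfall.** Section 11.2.2 does not state 0.7 as conditional on ECOG. If 0.7 is the hazard ratio of the planned analysis, the stated 85% to 86% stands and adjustment is an extra.
- **Size.** It rests on an ECOG mix and effect that the documents do not give. At modest ECOG effects the gain is within simulation noise.
- **Convention.** A treatment-only Cox model stratified by the randomization factors is defensible and matches the stratified log-rank test. Randomization-based inference already allows for chance imbalance.
- **Use elsewhere.** Text after the PFS paragraph in Section 11.5.2 is blacked out, so a supportive ECOG analysis cannot be excluded.

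All of these limit the point, but none removes it. The main hazard ratio model is stated in full and excludes ECOG. That hazard ratio is already conditional on three factors, so conditioning on a fourth is no real change of principle.

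**Conclusion.** The point holds as an improvement to how the hazard ratio is estimated; it is not an error in the plan. The OS and PFS Cox models omit a baseline value collected for every patient. If ECOG is prognostic, the reported hazard ratio is attenuated and can be moved by chance imbalance.

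Under assumed values (40% to 60% ECOG 1), an ECOG hazard ratio of 2.0 moves the OS estimate from about 0.71 to 0.70. An ECOG-adjusted test would gain about 3 to 5 power points. At an ECOG hazard ratio of 1.3 or less the gain is under 0.5 points, and at 1.0 there is none.

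The documents do not support saying that the confidence interval is too wide, that the confirmatory OS test is weakened by this sentence, or that ECOG is unused everywhere in the analysis. The SAP describes a discontinued trial with one patient and listings only. No hazard ratio will be estimated, and the practical consequence is confined to the protocol as a design.

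**What to change.** In the synopsis and in Sections 11.5.1 and 11.5.2, estimate the hazard ratio from the stratified Cox model with treatment and Screening ECOG (0 vs 1) as covariates, keeping the three randomization factors as strata. Report the treatment-only stratified hazard ratio alongside as a sensitivity analysis. Name the Screening value explicitly: Section 6.2.1 allows the first dose up to 5 calendar days after randomization, so a Cycle 1 Day 1 score can be recorded once the open-label allocation is known.

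The stratified log-rank test, combination weights, alpha levels and event numbers stay as they are. This edit therefore improves the reported hazard ratio and not the confirmatory power. Using the score test from the ECOG-adjusted model as the stage-wise OS statistic is a separate option. It would be needed to obtain the power gain, but it replaces the primary test statistic of an adaptive design and should be decided on its own merits.

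The cost is one model term and an edit in three places. The small downside is that the hazard ratio becomes conditional on ECOG as well as on the strata, and no longer corresponds exactly to the log-rank p-value; the treatment-only result covers that. The current SAP has no Cox sentence to change.
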